Detection and removal of colorectal adenomas is the recommended approach to the prevention of colorectal cancers (CRC). In separate studies we reported that water infusion in lieu of air insufflation (water method) provided a significantly higher overall adenoma detection rate (ADR) and proximal diminutive ADR than the usual method of air insufflation used during scope insertion. When indigocarmine was added to the water method, the dye highlighted small colonic lesions and significantly increased the overall ADR compared with historical cohorts examined by the water method alone or the conventional air method, as well as proximal diminutive ADR when compared with the water method alone. This proposal addresses the question of whether the water method (with or without indigocarmine) will result in a significantly higher proximal diminutive ADR compared with the air method alone in a RCT. The primary hypothesis asserts that a higher proportion with at least one proximal diminutive adenoma (ADR) will be found in the group randomized to the water + indigocarmine method compared with those randomized to the water method alone or the air method. Asymptomatic veterans referred for sedated colonoscopy for CRC screening at the Sacramento VAMC will be considered for enrollment. Over a 2.5 year recruitment period a total of 330 consented veterans will be randomized to confirm a 20% (34% - 14%) difference in proximal diminutive ADR in favor of the water group in the water vs. air comparison; and a 30% (64% - 34%) difference in favor of the indigocarmine + water method in the indigocarmine + water vs. water comparison. Consent covers agreement to undergo colonoscopy by the randomized methods, respond to pre- and post-colonoscopy questionnaires and allow the examination to be recorded for data analysis in a de-identified fashion. The PI, experienced in all three methods, will examine all enrolled patients. To ensure quality performance, all groups are expected to maintain the recommended overall ADR of 25% in male subjects and 15% in female subjects. Applicable human subject protection and adverse event monitoring procedures will be followed. Outcome data will be gathered and monitored prospectively and guarded by relevant data security measures. Appropriate evaluation with logistic regression and analysis of variance will be employed. Population studies showed that traditional air colonoscopy failed to eliminate post screening colonoscopy cancers or cancer mortality in the proximal colon. Even diminutive adenomas harbor significant dysplasia. A simple, inexpensive, easy-to-learn method of adding indigocarmine to the water method may increase the yield of proximal diminutive adenomas. A higher ADR may minimize the burden of interval CRC by decreasing missed adenomas. The long term goal is to perform further studies to determine if post screening colonoscopy interval cancers and cancer mortality in the proximal colon can be attenuated among the veteran population by the novel methods.

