The study will utilize proximal diminutive ADR as the primary outcome. Based on prior preliminary data (Tables 5 and 7), the proximal diminutive ADR is estimated to be 14%, 34%, and 64% for air, water and combined water with chromoendoscopy, respectively. The sample size needed to detect the smallest difference (between 0.14 and 0.34) is 103 per group ($\alpha = 0.05$, power 0.80), for a total of 309. To allow for possible sample loss (e.g. due to poor bowel prep), we plan to randomize 330 subjects with 110 in each group. With these samples we can significantly determine these differences, which are equivalent to 2.5 to 3 times greater observable risk between tests.

Flow Chart Based on CONSORT Guideline:

(c) Subject recruitment.

Screening

Patient sources will include referral from primary care providers, clinical reminder on CPRS, pre-colonoscopy clinic when patients choose colonoscopy and review of colonoscopy clinic schedule to identify eligible screening patients for study. Chart review will be performed by the research coordinator for selection of patients suitable to be recruited.

Contacting patients

The research coordinator will implement the following. Initial presentation/inform patients of study will take place via telephone contact or during open access colonoscopy class. Patients interested in participating in the study will receive either mailing (those contacted by phone) or hand-out (during educational sessions) of the explanatory information and consent form to review. The phone number to call the research coordinator for questions will be provided. Those expressing interest during the educational sessions will receive a separate briefing conducted by the research coordinator after colonoscopy class regarding details of the study. Patient identifiers (name and contact phone number) will be recorded to track and document acceptance or refusal.

Day of procedure

The research coordinator will review the study with the patient and obtain informed consent. Thereafter the investigator will review the indication for colonoscopy with the patient, exclude any previously overlooked contraindication, perform the necessary physical examination, discuss and address patient questions and have the patient sign the usual clinical informed consent for the colonoscopy procedure.

(d) Description of base population and groups to be studied and method of randomization.

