Demographic data interview & record review (co-variables)	X		
Medical and surgical history (co-variables)	X		
Complications - emergency department visit, hospitalization (co-variables)			X

(g) General analytic plan (statistical analysis):

Primary Hypothesis.

In patients undergoing sedated colonoscopy for screening, when all polypoid and flat lesions including diminutive ones proximal to the splenic flexure are removed by polypectomy or biopsy, the patients examined by the combined chromoendoscopy and water method will be found to have a higher proportion of individuals with at least one proximal diminutive adenoma compared with the water method alone or air insufflation method for aiding insertion of the colonoscope.

Statistical Analysis: We will summarize the variables collected by calculating the frequencies of the categorical variables [such as number of patients with at least one proximal diminutive adenoma (proximal diminutive ADR), number of adenomas detected, adenoma location, adenoma size, gender, ethnicity, etc) and calculating the mean and standard deviation of the continuous variables (such as adenoma size, volume of water used, age, BMI, etc)].

To investigate differences in ADR, we will use logistic regression models, with an outcome that is a binary variable denoting whether each subject had one or more diminutive proximal adenomas. These models will allow us to quantify the differences between the three tests and determine if the differences are statistically significant. We will account for demographic characteristics (age, gender, BMI, ethnicity, etc) and investigate how other primary covariates (procedure time, volume of water used in study, etc) affect the rate of adenoma detection. Following, we will investigate the effects of secondary covariates (colon cancer detected, sedation medications) on adenoma detection rates.

As a secondary analysis, we will investigate how the secondary outcomes vary among the three tests. We will use repeated measures ANOVA and logistic regression models to quantify the differences between tests and to determine if they are statistically significant.

Pitfalls and solution

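### The sample size section's "which are equivalent to 2.5 to 3 times greater observable risk between tests" does not follow from its own rates (risk ratios about 2.4, 1.9 and 4.6), and the analysis plan names no effect measure or interval for the primary outcome

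*Combined protocol and SAP*

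**What the plan says.** The sample size calculation (section (4)(b), item d) states that "the proximal diminutive ADR is estimated to be 14%, 34%, and 64% for air, water and combined water with chromoendoscopy, respectively". It continues: "The sample size needed to detect the smallest difference (between 0.14 and 0.34) is 103 per group", at alpha 0.05 and power 0.80, raised to 110 per group and 330 in all to allow for losses. Its last sentence describes the planned differences as ones "which are equivalent to 2.5 to 3 times greater observable risk between tests".

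The opening abstract puts the aim in percentage points. When water is set against air, the trial is "to confirm a 20% (34% - 14%) difference in proximal diminutive ADR in favor of the water group". For the further step of adding dye, the abstract plans for "a 30% (64% - 34%) difference in favor of the indigocarmine + water method", relative to water alone. The primary hypothesis in the abstract, the Specific Aims and section (g) also compares dye+water with air.

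For the primary outcome, section (g), General analytic plan, says "we will use logistic regression models, with an outcome that is a binary variable" for at least one proximal diminutive adenoma. The models are to quantify the differences between the three methods and test them. Demographic characteristics are to be accounted for, and the effects of other primary covariates, such as procedure time and water volume, are to be investigated. Table 10 lists volume of water, cecal intubation time, withdrawal time and total procedure time as primary covariates beside age, gender, BMI and ethnicity. Section (g) mentions no odds ratio, risk ratio, risk difference or confidence interval.

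**The concern.** There are two linked issues.

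First, the multiple in the sample size section can be checked against the three rates a few lines above it, and it fails. The clearest failure is dye+water vs water, where the detection rate does not quite double. A reader who relies on that sentence gets too favourable a picture of what adding dye to water is assumed to achieve.

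Second, the aim is in percentage points, the sample size remark is in multiples of risk, and the default output of the only named model is a conditional odds ratio. With rates between 14% and 64% these scales give very different numbers. Because the plan does not say which will be reported or with what interval, the choice could be made after the data are seen. A conditional odds ratio also depends on which covariates are in the model, and the covariate list is open-ended. If water volume or procedure time entered the primary contrast, the model would condition on quantities that the assigned method itself affects.

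**Working it through.** **Inputs.** Rates 0.14, 0.34 and 0.64 and 110 per group (sample size calculation); raw counts from Tables 5 and 7.

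**The plan's own figure.** The stated multiple is 2.5 to 3. The candidate scales are:

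| Contrast | Risk difference | Risk ratio | Odds ratio |
|---|---|---|---|
| Water vs air | 0.34 − 0.14 = 0.20 | 0.34/0.14 = 2.43 | (0.34/0.66)/(0.14/0.86) = 3.16 |
| Dye+water vs water | 0.64 − 0.34 = 0.30 | 0.64/0.34 = 1.88 | (0.64/0.36)/(0.34/0.66) = 3.45 |
| Dye+water vs air | 0.64 − 0.14 = 0.50 | 0.64/0.14 = 4.57 | (0.64/0.36)/(0.14/0.86) = 10.92 |

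No column gives 2.5 to 3.

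**Other readings tried**
- Relative increase (risk ratio minus 1): 1.43, 0.88 and 3.57.
- Ratio of non-detection: 0.86/0.66 = 1.30; 0.66/0.36 = 1.83; 0.86/0.36 = 2.39.
- Risk ratios from raw counts: Table 5, (26/92)/(13/90) = 1.96; Table 7, (18/28)/(10/29) = 1.86.
- Odds ratios from raw counts: Table 5, (26/66)/(13/77) = 2.33; Table 7, (18/10)/(10/19) = 3.42.

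**Rounding of the input rates.** Letting each rate move by half a point:
- Water vs air runs from 0.335/0.145 = 2.31 to 0.345/0.135 = 2.56, so 2.5 is a loose rounding at best.
- Dye+water vs water runs from 0.635/0.345 = 1.84 to 0.645/0.335 = 1.93 and cannot reach 2.5.

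**Does the multiple affect the sample size?** No. The calculation uses 0.14, 0.34, alpha and power; the multiple comes afterwards as commentary. Whether 103 follows from those inputs is a different question (the usual two-sided formula gives 71 per group, or 81 with continuity correction) and is not part of this point.

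**Scale and order.** Dye over water is the larger of the two planned steps in percentage points (30 vs 20) and in odds ratios (3.45 vs 3.16), but the smaller in risk ratios (1.88 vs 2.43). The sample size section calls 0.14 vs 0.34 the smallest difference, which is true in percentage points. It then describes the effects as multiples of risk, the scale on which that same contrast is the larger of the two.

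**What an interval would show.** At the planned rates, with all 110 per group analysed and no adjustment, the half-width of a 95% interval is 1.96 × √[(p₁q₁ + p₂q₂)/110], where q = 1 − p:
- Water vs air: 1.96 × √[(0.1204 + 0.2244)/110] = 0.110, so 20 points would carry an interval of about 9 to 31.
- Dye+water vs water: 1.96 × √[(0.2304 + 0.2244)/110] = 0.126, so 30 points would carry about 17 to 43.

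A significant test alone would not tell the reader this.

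**Timing of the covariates.** Randomisation is immediately before insertion. Age, gender, BMI and ethnicity precede it, as does completion of the split preparation. Water volume, cecal intubation time, withdrawal time and total procedure time follow it. So does cancer found at the examination, which the response to Critique 3 says will be taken into account when the differences are estimated.

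**The case against.** Several stronger readings are tempting, and the documents do not support them.

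- **That the trial analyses odds ratios.** No section says so. Section (g) says the models will quantify differences and leaves the scale open. The one odds ratio in the documents, in the Rationale, is a collaborator's result reported beside its raw percentages. Risk differences can be derived from the same logistic model.
- **That sizing on proportions conflicts with testing by logistic regression.** It does not. Both address the null of equal detection rates.
- **That formal 20- and 30-point hypotheses go untested.** The stated hypothesis is directional, a higher proportion with dye+water. The 20 and 30 points are planning differences, although the abstract does speak of confirming them.
- **That percentage-point results will be unavailable.** Section (g) begins by tabulating the number of patients in whom the outcome is found, so a crude difference can be worked out. What is missing is a named measure with an interval.
- **That effects will be overstated by 30% or 83%.** Those figures (3.16/2.43 = 1.30; 3.45/1.88 = 1.83) describe a future reader mistaking a crude odds ratio for a risk ratio. Nothing in the plan makes that mistake. That scales rank the steps differently is a mathematical property, not an error in the plan.
- **That the primary contrast will be adjusted for water volume or procedure time.** Section (g) can be read as adjusting for demographics first and examining the other covariates afterwards, and the response to Critique 3 describes the covariate work as a follow-up. The text leaves this open.

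These objections narrow the point but do not remove it. The multiple is still wrong, and the effect measure, the interval and the covariate set of the primary model are still unspecified.

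**Conclusion.** The point holds in a limited form. On the plan's own rates the multiple should read about 2.4 for water vs air, 1.9 for dye+water vs water and 4.6 for dye+water vs air. Rounding can stretch the first to about 2.5 but cannot rescue the second. The primary analysis names a model but not what will be estimated from it, and it does not clearly separate baseline covariates from those that follow randomisation.

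This is minor. Neither 103 nor 330 depends on the multiple, and the null hypothesis and its test are unaffected. The conclusion about the multiple takes 14%, 34% and 64% as given. The conclusion about the effect measure rests on the text of section (g) and Table 10, with no more detailed statistical plan in the documents.

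**What to change.** In the sample size calculation, replace the multiple with the risk ratios that the rates imply: about 2.4 (water vs air), 1.9 (dye+water vs water) and 4.6 (dye+water vs air).

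In section (g), state three things:
1. For each of the three contrasts, the standardised risk difference with a 95% CI will be reported, with the odds ratios alongside. It is obtained by averaging the model's predicted probabilities over all patients under each method and taking differences.
2. The model for these estimates adjusts only for named variables fixed before randomisation, such as age, gender, BMI and ethnicity, with no open-ended list.
3. Models that include water volume or procedure time are exploratory. The same should apply to other variables that arise after randomisation.

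The cost is a few sentences, one routine post-estimation step on a model already planned, and a less favourable stated multiple for dye+water vs water. Design, sample size and data collection stay as they are.

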19. **Budget:** Response: Critical reviewers have raised concerns over the accuracy of the real time recordings. The DVD recording (e.g. biopsy duration, polypectomy durations etc) provides more objective and "accurate" measurements. Nevertheless, we have made adjustment (reduction) to the expenses for the study.

20. **Overall Evaluation:** Response: The clinical implication is detection of more adenomas may translate into fewer missed but potentially precancerous lesions. The revised application has added preliminary data to address the Reviewer's concerns.

Critique 3

Statistics

1. Response: The revised application involves a single colonoscopist and enrollment of only first time screening colonoscopy patients. The statistics section has been revised accordingly.

2. Response: see response above.

3. Response: The statistical analysis has been entirely rewritten. We investigate the primary hypothesis through logistic regression models. To follow up, we investigate how covariates affect the rate of adenoma detection. Our secondary analysis uses repeated measures regression models to investigate how secondary outcomes (adenoma size, adenoma location, etc) vary between the three methods.

4. Response: Because patients are sedated, and will be given additional sedation medication throughout the procedure if requested, we do not expect large numbers of drop-out (failure to complete colonoscopy). However, patients that do drop out will be retained and assigned a value of zero for the number of adenomas detected, if none is found in the examined segments.

5. Response: The analyses are designed to quantify the differences between the three treatment groups and to determine if they are significant. Additionally, we plan to account for the rate of colorectal cancer diagnoses in the estimation of the differences between the three tests.

Specific Aims

(a) Goal

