Population studies showed that traditional air colonoscopy failed to eliminate post screening colonoscopy cancers or cancer mortality in the proximal colon. Even diminutive adenomas harbor significant dysplasia. A simple, inexpensive, easy-to-learn method of adding indigocarmine to the water method may increase the yield of proximal diminutive adenomas. A higher ADR may minimize the burden of interval CRC by decreasing missed adenomas. The current study evaluates the benefits of a combined chromoendoscopy and water method for screening colonoscopy in identifying proximal diminutive adenomas compared to the water method alone and the conventional air method. The long term goal is to perform further studies to determine if post screening colonoscopy interval cancers and cancer mortality in the proximal colon can be attenuated among the veteran population by the novel methods.

(b) Hypothesis

In patients undergoing optical colonoscopy for first time CRC screening, a higher proximal diminutive ADR (proportion of patients with at least one diminutive adenoma in the colon proximal to the splenic flexure) will be found in the group examined by combined chromoendoscopy (indigo carmine) with water method compared with water method alone or air method.

Primary outcomes: Proximal diminutive (<10 mm) adenoma detection rate.

Secondary outcomes: ADR (overall for entire colon and for proximal colon), cecal intubation success rate, sedation medications.

Co-variables: patient demographic variables [age, gender, BMI, co-morbidity, endoscopic findings, etc.], successful completion of split bowel preparation

(c) Specific Objectives

To compare the primary and secondary outcomes in a prospective RCT involving the combined chromoendoscopy with water method vs. water method alone and air method in asymptomatic patients undergoing first time outpatient screening colonoscopy.

Short title: Comparative efficacy of water & indigo carmine vs. water or air method on ADR – a RCT

Long title: RCT to compare proximal diminutive adenoma detection rate (ADR) of combined chromoendoscopy (Indigo carmine) with water infusion in lieu of air insufflation (water method) vs. water method alone or conventional air method in screening colonoscopy

(1) Rationale

Statement of the Problem

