Block randomization using computer-generated random numbers will be used to ensure random, balanced allocation to the three study arms. The randomly assigned treatment options are contained in sequentially numbered, sealed opaque envelopes. A sealed envelope will be opened immediately before the procedure, and the assigned intervention will be performed accordingly. The endoscopist will be blinded to the assignment until the randomization envelop is opened. Patients will be blinded to the randomization. The monitor will be blocked from the patient's view by using a towel to cover the patient eyes on scope insertion (acceptable to patients in the several RCT conducted at the Sacramento VA site).

Colonoscopy

Before the start, during and after the examination, upper arm blood pressure, finger oximetry, and cardiac rhythm will be monitored to document complications, if any (e.g. hypotension, hypoxia, arrhythmias) with monitoring systems (IntelliVue MP40, Philips). The PI will perform all study cases for this protocol to obviate limitations in variability of endoscopist performance. At the beginning of the examination, the patient will lie in the left lateral position with the hip flexed. After digital rectal examination to exclude obstruction or anal lesions, the colonoscope will be inserted. For all patients, application of abdominal compression, change in patient position, loop reduction maneuvers will be employed at the clinical discretion of the colonoscopist (usual practice). All adjunct maneuvers will be recorded. Rescheduling due to poor bowel preparation or failed procedure will be recorded.

Control method

1. Conventional air insufflation method will be used.

Study methods

1. Usual water method will be used (as described below).
2. The usual water method combined with chromoendoscopy (0.008% indigo carmine).

Cecal intubation is arrival in the cecum and visualization of the appendix orifice (Figure 3) and/or ileal cecal valve (in patients with appendectomy) under water, subsequently confirmed after air insufflation. The time of insertion, cecal intubation, findings and time of withdrawal from the rectum will be recorded by endoscopic photographs [60] using standardized equipment. A digital video recording of the entire procedure is taken to provide objective documentation/verification of time intervals and endoscopic findings.

Sedation protocol during colonoscopy

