If the cecum is believed to have been reached, but the usual landmarks are not recognizable, more water is infused to distend the cecum to aid visualization of the appendix opening. The volume of infused water, the use of position change and abdominal compression will be recorded. Once the appendix opening is visualized, air insufflation will be used to distend the cecum to confirm touching of the cecal floor with visualization of the ileocecal valve and/or the appendix orifice (cecal intubation). Thereafter, usual air insufflation will be used to facilitate suctioning of residual colonic content (mostly water and residual feces) and mucosal inspection, biopsies or polypectomy during endoscope withdrawal. All polyps (including diminutive ones in the right colon) will be removed and tissue submitted for pathological evaluations. When multiple diminutive polyps (predominantly hyperplastic) in the rectum are identified and recorded; a limit of one biopsy will be taken (to minimize time burden on study subjects).

Reassuringly, water enemas using equivalent volumes were not associated with significant fluctuations in serum electrolytes [63]. Preliminary data did not show any significant change or differences in the serum electrolytes level before and after the water infusion (Table 8) [58]. With the suction of dirty water and then infusion of clean water during scope advancement, the actual amount of water within the colon at any time during scope insertion is much less than the total volume of water used to facilitate scope passage.

The combined chromoendoscopy with indigo carmine and water method: As used in pilot study, the technique is identical to the water method above except we add 10 ml of 0.8% indigo carmine solution into a liter bottle of sterile water to make up a solution of 0.008% indigo carmine [22].

b. Population to be studied

Inclusion criteria: asymptomatic veterans scheduled for first time screening colonoscopy and agree to be randomized will be enrolled.

Exclusion criteria: patients who decline to be randomized, non screening cases.

c. Unit(s) of analysis (Table 10).

Table 10: Primary and secondary outcome variables

Measures	Details
Primary Outcome	
Proximal diminutive adenoma	1 = yes, 0 = no
Primary covariates	
Demographic variables	Age, gender, BMI, ethnicity
Volume of water (ml)	ml used during colonoscopy
Cecal intubation time*	Time from anus to cecum (appendix opening, ileocecal valve seen)

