Withdrawal time*	Time from cecum to anus
Total procedure time*	From insertion of colonoscope to removal from the anus
Completion of split preparation	Yes = 1, no = 0
Secondary covariates	
Colon cancer	Colon cancer discovered during exam (Yes = 1, no = 0)
Sedation medications	Type, initial dose, additional doses during colonoscopy based on patient pain score and request
Secondary Outcomes	
Size of adenoma*	mm measured by open forceps
Anatomical location of adenoma	rectum, sigmoid, descending, splenic, transverse, hepatic, ascending, cecum
Located behind a fold*	Yes = 1, no = 0
Morphology of lesion*	Polypoid or flat
Pathologic diagnosis of the biopsy or snared polypectomy specimen	Adenoma (with or without advanced features), hyperplastic polyp, serrated adenoma
Immediate complications	Perforation, bleeding, hypoxia, hypotension, arrhythmia
Complications up to 30 days	Perforation, bleeding, hypoxia, hypotension, arrhythmia, severe abdominal pain requiring ER visit and/or admission to hospital

* Documented during colonoscopy and objective confirmation by digital video record of endoscope clock.

Record keeping: A digital image capturing system will be used to record the procedure to document the procedure times (insertion, arrival in the cecum, biopsy, polypectomy, end of examination), confirmation of cecal intubation (visualization of the appendix orifice and/or the ileocecal valve) and the findings during the withdrawal phase (recorded by the research assistant). The digital images will bear no personal identifier.

d. Sampling strategy

[figure not shown]
The consent covers agreement to allow the colonoscopist to randomize the method to aid colonoscope insertion and examination (chromoendoscopy with water vs. water method vs. air insufflation), and to video record and photograph the procedure for analysis.

In order to accommodate the patients and allow them time to complete the split bowel preparation in the morning of the procedure, the study procedures will be scheduled as late morning and early afternoon cases as this will give the patients more time to complete the bowel preparation.

Sample size calculation

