5-10 mm adenomas and in 1.7% of ≤4 mm adenomas [67]. It is logical to expect that with the adenoma-cancer sequence concept, a proportion of small polyps can grow/evolve to become dysplastic and eventually cancer. Therefore even small lesions especially those on the right side should be biopsied or removed because of the potential risk of future malignancy [7,8]. Once detected on screening colonoscopy and confirmed pathologically, the finding (adenomas or flat lesions) would change the recommendation for subsequent surveillance. The lack of mortality reduction by optical colonoscopy for right-sided cancer has not been explained and this may be related to miss lesions. These considerations justify the detection and removal of diminutive lesions during optical colonoscopy, especially those in the right colon. However, only long term follow up studies will be able to show if removal of the right-sided small adenomas will prevent future development of colon cancer. We will continue to follow this cohort of patients when they return for surveillance colonoscopy or with symptoms of colorectal cancer.

The presence of poor bowel preparation could limit examination. The presence of stool could change the color of the indigo carmine solution turning it green instead of blue color. We emphasize the need for suction removal of the dirty water from the colonic lumen before infusion of clean (colored) water to clear the view for visualization and enhance the staining effects of indigo carmine. Dye staining serves to highlight the contour and contrast between the polyp and adjacent mucosa thus improving observation of the lesions.

Other issues

Issues related to expectation. Expectation of benefit (e.g. finding more lesions) cannot be avoided by the colonoscopist who is not blinded. We'll monitor changes in process variables (variables that reflect the presumed mechanism of treatment, e.g. cecal intubation documented by photograph of the appendix orifice and or cecal folds, withdrawal time, rate of adenoma detection (e.g. control group should meet the quality standard of having an ADR of 25% in male patients undergoing screening).

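### The terms of the primary logistic model are not fixed, and water volume and procedure times, which arise after randomisation, are classed as primary covariates without being excluded from the arm test

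*Combined protocol and SAP*

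**What the plan says.** Section (4)(g) uses logistic models, in the plural, for the binary primary outcome and states: "These models will allow us to quantify the differences between the three tests and determine if the differences are statistically significant". It then accounts for demographics (a list left open with an 'etc') and, in the same sentence, will "investigate how other primary covariates (procedure time, volume of water used in study, etc) affect the rate of adenoma detection". Cancer found and sedation are examined in a later step.

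Three other places bear on the model terms:

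- **Table 10** puts volume of water ("ml used during colonoscopy"), cecal intubation time, withdrawal time ("Time from cecum to anus") and total procedure time under the heading Primary covariates, together with the demographics and completion of the split preparation.
- **Specific Aims (b)** has a different list: "Co-variables: patient demographic variables [age, gender, BMI, co-morbidity, endoscopic findings, etc.], successful completion of split bowel preparation". It names neither volume nor times, but it does name endoscopic findings.
- **Response to reviewers, Critique 3, item 5** says: "we plan to account for the rate of colorectal cancer diagnoses in the estimation of the differences between the three tests".

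On timing, the Randomization section says: "A sealed envelope will be opened immediately before the procedure". On mechanism, the part of Other issues that deals with expectation counts withdrawal time among "process variables (variables that reflect the presumed mechanism of treatment".

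**The concern.** Volume, times and findings are all observed after the envelope is opened. Volume is largely set by the assigned method: the water arms are inserted with water, while the air arm only irrigates on withdrawal. Section (e) attributes better detection to the water exchange itself. An arm odds ratio adjusted for volume or time therefore does not answer the trial's question, which is whether a method finds more patients with a proximal diminutive adenoma.

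Because no model is named as primary, an analyst could follow Table 10 literally, or choose among models after seeing the data, without departing from the plan. The most exposed contrast is water versus air, which sets the sample size and is a confirmation aim in the abstract. Dye + water versus air, part of the stated primary hypothesis, is open to the same bias.

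**Working it through.** **1. The plan's own figure.** Sample size calculation: 14% vs 34%, alpha 0.05, power 0.80, 103 per group. With the pooled two-sided formula, mean rate 0.24:

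n = [1.96 × √(2 × 0.24 × 0.76) + 0.842 × √(0.14 × 0.86 + 0.34 × 0.66)]² / 0.20² = (1.184 + 0.494)² / 0.04 ≈ 71 per group (81 with continuity correction).

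The stated 103 is not reproduced. It is larger than its inputs require, so this is not an under-powering error, and nothing below rests on it.

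**2. Arm-only model, 110 per arm.** Two-sided 0.05: power 94% for water vs air and 99.5% for dye + water vs water.

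**3. Volume added, no effect on detection (collinearity alone).** Water-arm volume is 1817 ± 679 ml (Work Accomplished, item 8; 37 patients). The ± is read as an SD, since as a standard error it would imply an SD of 679 × √37 ≈ 4130 ml. Air-arm volume is not given; 0, 100 ± 100 and 500 ± 300 ml are assumed. Simulated water-vs-air estimates, with power ≈ Φ(log OR / SE − 1.96):

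| Model | log OR (SE) | Approximation | Simulated power |
|---|---|---|---|
| Arm only | 1.16 (0.34) | Φ(1.45) = 93% | 94% |
| + volume, air 0 ml | 1.17 (0.52) | Φ(0.29) = 61% | 62% |
| + volume, air 100 ml | 1.17 (0.50) | Φ(0.38) = 65% | 65% |
| + volume, air 500 ml | 1.18 (0.44) | Φ(0.72) = 76% | 77% |

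Across independent runs the range is about 62-79%. The normal distribution puts 39% of patients above 2000 ml, because (2000 − 1817)/679 = 0.27, whereas the description of the water method gives a range of 200-2000 ml. With volume uniform over that range, power is 71%, 76% and 88% (about 71-90% across runs).

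**4. Volume related to detection within an arm (illustration only; slopes assumed).** With air-arm volume 0, the adjusted log odds ratio moves by about −b × (mean difference / SD), where b is the log-odds change per SD. The ratio is 1817/679 = 2.68, or 1100/520 = 2.12 for the uniform case.

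- *Detection falls with volume* (more water in a dirtier colon), OR 0.8 per SD: b = −0.223, shift +0.223 × 2.68 = +0.60. With truly equal arms, water or dye + water is falsely favoured over air in about 21-28% of trials (12-22% with uniform volume), against a nominal 2.5%.
- *Detection rises with volume* (water exchange cleans the colon), b = +0.2: shift −0.54, so 1.16 − 0.54 = 0.62 and Φ(0.62/0.52 − 1.96) = 22%. Simulated water-vs-air power is 22-39%, and dye-vs-air power is 96-99.7%.

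The documents offer a rationale for either sign. Dye + water vs water keeps about 98% power or more throughout, because both arms use water in the same way.

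**5. Times.** The documents give no time differences by arm, so no size can be derived. As an illustration, assumed extra water-arm withdrawal minutes of −1, 0, 1 and 2 give water-vs-air power of 99%, 93%, 71% and 38% when gross withdrawal time is fitted.

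**6. Cancer.** Critique 3, item 5 puts cancer diagnoses into the arm contrast, while section (g) examines them afterwards. Reading these as cancers found at the examination relies on the Table 10 definition. Cancer will be rare, so the effect is small.

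**The case against.** A reader might infer that the plan commits to adjusting the arm effect for water volume and procedure time. The documents do not support that:

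- Section (g) accounts for demographics but only investigates how volume and time act.
- Critique 3, item 3 introduces the covariate work as a follow-up to the primary hypothesis.
- Critique 2, item 6 treats additional observations as hypothesis-generating.
- The Specific Aims list contains neither volume nor times.
- Critique 2, items 14-15 and the Other issues section give time a quality-monitoring role.

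Together these favour the exploratory reading, and that part of the objection stands.

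It also stands that the slope and time scenarios rest on assumed inputs, and that the collinearity loss is modest if volume is spread evenly over 200-2000 ml.

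What does not follow is that the matter is closed. None of these phrases fixes the terms of the arm test, while Table 10 and section (g) call volume and time primary covariates. Nor can a sensible default be assumed. The Statement of the Problem presents a collaborating site's water-vs-air odds ratio of 1.81 as independent of withdrawal time and preparation quality. The crude value from 57% vs 46% is (0.57/0.43)/(0.46/0.54) = 1.56, so that figure appears to be an adjusted one.

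**Conclusion.** The concern holds as an unresolved ambiguity that should be closed before analysis. The plan does not say which logistic model supplies the primary arm effect, and it does not exclude variables that arise after randomisation and partly reflect mechanism.

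The size closest to the documents' own figures is the collinearity case: water-vs-air power of about 62-79% (71-90% with uniform volume) instead of about 94%, against a planned 80%. It assumes an air-arm volume of 0-500 ml and 110 analysed per arm. Beyond that, both air contrasts could be biased, but the documents fix neither direction nor amount.

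Two stronger readings should be resisted. The primary hypothesis is not undermined as a whole: dye + water vs water is practically unaffected, and dye + water vs air keeps at least 96% power except at the steepest positive slope tried (+0.4 per SD, 73-97%), although it shares the false-positive risk in step 4. Nor is the cancer statement a material source of error; it is an inconsistency to tidy.

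**What to change.** 1. In (4)(g), state that the primary arm test comes from one logistic model with arm plus a closed list of pre-randomisation covariates: age, gender, BMI, ethnicity and, if wanted, baseline co-morbidity and completion of the split preparation (finished before the envelope is opened). Replace each 'etc' with that list.
2. Split the Table 10 heading Primary covariates into baseline covariates and procedural (post-randomisation) variables.
3. State that models containing water volume, procedure times, sedation, cancer found or endoscopic findings are exploratory. They may include arm, but they do not supply the primary arm effect.
4. Align Critique 3, item 5 and the Specific Aims co-variable list with this: cancer diagnoses do not enter the primary contrast, and endoscopic findings are not a covariate in it.

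The cost is wording only, with no new data, visits or patients. The exploratory work is kept, and if the sponsor already intends this reading, the change merely records it.
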